### Aims

The first aim of this study is to highlight possible psychosocial clusters of variables that are specific to the onset and maintenance for each condition (FM, CM, and VU). Specifically, the observation of possible clusters will be made based on variables such as personality traits, defense mechanisms, central sensitization, and childhood traumatic experiences. The hypothesis is that specific psychological factors (clusters of high number of early traumatic events, high levels of central sensitization, and specific traits and defense mechanisms) characterize FM, CM, and VU groups compared to controls reporting other types of CP (e.g., knee arthrosis, rheumatoid arthritis).

A second aim, to give directions for tailored psychological treatments devoted to these conditions, is to explore the association between FM, CM, and VU with depression, anxiety, somatization, quality of life, alexithymia, social support, sexual satisfaction, and functioning. In line with our hypothesis that each of

these conditions has specific areas of psychological sensitivity, this will make it possible to identify specifically for each condition the areas of greatest interest that can be investigated and treated in clinical intervention.

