## MEASURES

The study involves the administration of a protocol of self-report questionnaires consisting of two parts: the main (about 25 minutes for the administration) and the optional one (additional 20 minutes). This decision stems from the realization of the length of the protocol, to increase the collection of data in pursuit of the main objective of the study (cluster analysis).

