#### STATYSTICAL PLANNED ANALYSES

The required sample size was estimated a priori for the ANOVA procedure that tested the cluster model sensitivity having 4 groups (migraine, fibromyalgia, vulvodynia, and controls). Using the G\*power program,  $p = 0.05$ , statistical power of 85%, and effect size of 0.35, the calculation yielded a total sample size of  $n = 108$  participants per group (432 as total) The four centers involved in the recruitment of the participants will be the Università di Milano IRCCS Sant'Ambrogio Galeazzi under the head of [name] and Dott. [name], the IRCCS Mondino di Pavia under the head of [name] and [name], The Policlinico San Matteo of Pavia under the head of [name] and Dott. [name], and the Policlinico Umberto I of Sapienza University of Rome under the head of Dott. [name].

ANOVAs and  $\chi^2$  analyses will be carried out to compare groups on sociodemographic characteristics for descriptive reasons and to select possible covariates based on selection bias.

A group of cluster analyses will be performed to classify the samples based on personality traits, defense mechanisms, central sensitization, and childhood traumatic experiences (twenty-two variables corresponding to total scores and thematic subscales of the related measures), aiming to identify different clinical phenotypes within the study samples. A statistical procedure of Two-Step Cluster Analysis will be preferred due to its ability to ensure that one variable does not dominate the cluster solution. Furthermore, it enables the user to identify the importance of each item in the cluster solution. The model fit will be assessed by Schwarz's Bayesian Information Criterion and evaluated by the average silhouette coefficient, an internal validity index representing cluster cohesion and separation quality, ranging between 0 and 1; the closer to 1, the better the model.

Crosstab analyses will be performed to test the association and their strength, and MANOVAs to detect differences in the classification variables based on cluster groups, and Pearson's correlation to explore associations among clusters and other psychological domains. The statistical analyses will be performed using IBM SPSS v. 27.0 and AMOS v.22 (SPSS Inc., Chicago, IL, USA).

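### The sample-size statement calls 108 both a total and a per-group number; with Cohen's f = 0.35 the stated inputs require 108 in total, not 432

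*Combined protocol and SAP*

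**What the plan says.** The Statistical planned analyses section opens with the calculation: "The required sample size was estimated a priori for the ANOVA procedure that tested the cluster model sensitivity having 4 groups", namely migraine, fibromyalgia, vulvodynia and controls. It was done in G*Power with p = 0.05. The text continues: "statistical power of 85%, and effect size of 0.35, the calculation yielded a total sample size of" 108 "participants per group (432 as total").

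The effect size is given only as 0.35. The plan does not say whether this is Cohen's f, f², eta² or d. It gives no dropout allowance, multiplicity adjustment or other inflation, and no other section states a sample size.

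Two other statements bear on how 432 should be read. The Measures section says the questionnaire was split into main and optional parts to increase data collection "in pursuit of the main objective of the study (cluster analysis"). The Statistical planned analyses section bases that cluster analysis on "twenty-two variables corresponding to total scores and thematic subscales of the related measures".

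**The concern.** One number carries two incompatible labels in one sentence. The bracketed 432 is 4 × 108, so the per-group reading is the one the plan acts on. For a one-way ANOVA, however, the usual result of such a calculation is a total across groups. If 108 was that total, reading it as a per-group number inflates the requirement fourfold.

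This is the plan's whole justification for its size. If the stated inputs do not lead to 432, the plan does not say what effect 432 was chosen to detect, and anyone quoting the calculation in a report will quote one that does not reproduce. The unnamed metric also matters: under one reading of 0.35 the study is far larger than the ANOVA needs, and under another it could fall short of the stated 85% power.

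**Working it through.** **Inputs** (all from the Statistical planned analyses section): k = 4 groups, alpha = 0.05, target power 0.85, effect size 0.35 with no metric named, equal groups implied by 4 × 108 = 432.

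**Method.** For the one-way ANOVA omnibus test with total N,

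Power = P( F′(3, N − 4, λ) > F₀.₉₅(3, N − 4) ), with λ = N·f².

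The required N is the smallest multiple of 4 with power of at least 0.85.

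**Reading 1: 0.35 is Cohen's f (assumption).** f² = 0.1225.

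| N total | per group | λ = 0.1225·N | power |
|---|---|---|---|
| 100 | 25 | 12.25 | 0.832 |
| 104 | 26 | 12.74 | 0.848 |
| 108 | 27 | 13.23 | 0.863 |
| 432 | 108 | 52.92 | 0.999998 |

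The plan's own figure of 108 is reproduced exactly, but as a total. The stated inputs do not give 432. Solving power = 0.85 at N = 432 gives f = 0.1695, about half the stated 0.35.

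**Reading 2: 0.35 is f² or eta².** f² = 0.35 requires 40 in total. Eta² = 0.35, so f² = 0.35/0.65, requires 28. Neither gives 108 or 432.

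**Reading 3: 0.35 is Cohen's d, taken as the range of the four means.** The plan does not mention d. Here f is the population SD of the four means, in units of the within-group SD, and depends on their pattern.

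| pattern of means | f | required N | power at 432 |
|---|---|---|---|
| 0, 0, d, d | 0.175 | 408 | 87.4% |
| 0, d, d, d | 0.152 | 540 | 75.3% |
| 0, d/3, 2d/3, d | 0.130 | 728 | 60.9% |
| 0, d/2, d/2, d | 0.124 | 808 | 55.9% |

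None returns 432. It appears only if f = 0.175 is truncated to 0.17 before entry: f = 0.17 gives 84.9% at 428 and 85.2% at 432. Rounding up to f = 0.18 gives 384. The plan states no such step.

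**Reading 4: d = 0.35 for a single pairwise comparison.** This needs 148 per group two-sided or 119 one-sided, not 108. Bonferroni adjustment for 3 or 6 comparisons raises it to between 165 and 223 per group.

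**A stricter alpha as the missing step.** With f = 0.35, alpha/6 requires 152 in total and alpha/22 requires 184. Neither explains 432.

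**The case against.** The strongest reply is that little is at stake. The operative target is clear, since 4 × 108 = 432 and the double label may be loose English. A statistician who sees G*Power, ANOVA and 0.35 will assume Cohen's f and recover the calculation. Under that reading the study is larger than needed, no estimate or conclusion changes, and the correction is only wording. The Cohen's d scenarios have no support in the text.

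Much of this stands. The target is not in doubt, f is the likeliest metric, and on that reading the error does no harm to power. The d scenarios show only that the metric needs naming; they are not evidence of what was done. Which pattern of means fits the study is also open. The Aims section has specific factors that "characterize FM, CM, and VU groups compared to controls reporting other types of CP", which suggests one group against three, but it also expects each condition to have its own profile.

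The reply does not supply a route from the stated inputs to 432. Recovering the calculation under f shows that its answer is 108 in total. That the target is large enough anyway is also secure only if the metric is f, which the plan does not say.

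A related point deserves weight: apart from the sizing sentence, the only ANOVAs in the section compare sociodemographic characteristics, and differences between clusters are to be tested by MANOVA. The sized four-group ANOVA therefore has no named outcome.

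**Conclusion.** The concern holds. The double label and the missing metric are plain in the text and need no assumption. If 0.35 is Cohen's f, the requirement is 108 in total (27 per group), and 432 is four times that (432/108 = 4). A total read as a per-group number and multiplied by four would explain 432, but that is an inference from the exact match; the plan does not state it.

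Under the f reading the error is in the safe direction. If 0.35 were a d range, power at 432 would run from 55.9% to 87.4% depending on the pattern of means, so the conclusion about size rests on the metric.

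This should be fixed as a documentation error. It is not a case for a smaller study, because the ANOVA minimum says nothing about what the 22-variable cluster analysis requires.

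**What to change.** Name the effect-size metric and give 108 one label. If the metric is Cohen's f, wording such as this would do:

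> For Cohen's f = 0.35, alpha 0.05, 85% power and 4 groups, the required total is 108 (27 per group). The recruitment target is 432 (108 per group) because [sponsor's reason, for example the needs of the 22-variable cluster analysis, if that is the reason]. With 432 participants, a 4-group ANOVA has 85% power for f of about 0.17.

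If the metric is Cohen's d, state the f that was entered and the assumed pattern of the four means. In either case it would help to name the outcome to which the sized ANOVA applies.

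The cost is two or three sentences. Recruitment and data collection do not change, and the target should not be reduced on this ground.

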
## VULVODYNIA

Vulvodynia is a condition that occurs in 8-10% of women of all ages (Arnold et al., 2007; Harlow et al., 2014) and is characterized by localized pain in the vulva, either spontaneous or upon touch, and can occur during sexual and/or non-sexual situations (Bergeron et al., 2020). Vulvodynia has a negative effect on the quality of life of women and their partners and imposes a profound personal and social economic burden. The diagnosis is established through a careful history and pelvic examination, including the cotton swab test, based on persistent vulvar pain lasting more than 3 months without an identifiable cause and with several potential associated factors. These include musculoskeletal and neurological factors, comorbid pain syndromes (such as fibromyalgia, chronic migraine, and irritable bowel syndrome) and psychosocial factors (Reed et al., 2012; Wesselmann et al., 2014; Bergeron et al., 2020). Current literature suggests that the onset and maintenance of vulvodynia likely involves a complex interplay of peripheral and central pain mechanisms, pelvic floor muscle and autonomic dysfunction, anxiety, depression, and adverse childhood events, as well as cognitive-affective, behavioral, and interpersonal factors (Bergeron et al., 2020). Vulvodynia has traditionally been conceptualized in a dualistic manner, arising from either physical factors or psychological and sexual difficulties, although research contrary to this concept and other hypotheses suggest that these two perspectives should be combined. Therefore, future studies should move in this direction, seeking to identify specific pathophysiological mechanisms within the framework of a biopsychosocial model. Indeed, a more recent theorization has focused on an integrated model that considers the interdependence of biopsychosocial factors in vulvodynia and associated disorders, in which medical and psychosocial mechanisms are considered to contribute to the onset, chronicization and exacerbation of pain and associated difficulties (Bergeron et al., 2011). The neurophysiology of vulvodynia is multifaceted and is characterized by both peripheral and central sensory abnormalities (Wesselmann et al., 2014; Pukall et al., 2016). Furthermore, increased sensitivity to different sensory modalities at extragenital sites has been demonstrated in women with vulvodynia (Giesecke et al., 2004; Foster et al.,

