#### *Inclusion criteria:*

- age range 18-65 years
- education > 5 years
- diagnosis of FM according to Wolfe, 2016
- diagnosis of CM according to Olesen, 2017
- diagnosis of VU according to Bornstein et al., 2016

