#### *Optional questionnaires (the participant decides whether to complete them)*

- Brief Symptom Inventory (BSI-18) (Franke et al., 2017): an abbreviated version of Derogatis' Brief Symptom Inventory, contains the three six-item scales of Somatization, Depression, Anxiety and the Global Symptom Score (GSI).
- SF-12 - Quality of Life Assessment (Apolone et al., 2001): The SF-12 is a generic short-form health survey developed in the United States from the original SF-36. It produces two summary measures for the assessment of self-perceived physical and mental health that are interchangeable with those of the SF-36.

- Toronto Alexithymia Scale (TAS-20) (Bagby et al., 1994): The Toronto Alexithymia Scale is a 20-item self-administered questionnaire that measures difficulty in identifying and describing emotions, which is an important part of alexithymia.
- Chronic Pain acceptance Questionnaire (CPAQ-8) (Fish et al., 2010): is an 8-item inventory measuring the acceptance of chronic pain.
- SPQ - Social Support Questionnaire (SPQ) (van der Lugt et al., 2012): is a short measure of perceived social support in relation to pain.
- Sexual Satisfaction Scale (SSS) - Short form) (Meston & Trapnell, 2005): represents a short 6-item measure of sexual satisfaction and discomfort.
- Short Form McGill Questionnaire (SF-MGQ) - Adapted for genito-pelvic pain (Melzack & Raja, 2005). Represents a qualitative and quantitative measure of pain, adapted to the genito-pelvic area.
- Female Sexual Function Index (FSFI) (optional) and International Index of Erectile Function (IIEF) (optional) (Rosen et al., 1997; 2000): represents a differentiated questionnaire for females and males on sexual function (desire, arousal and orgasm and satisfaction).

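### The vulvodynia group is all women and the other groups may include men, but no planned analysis uses sex, so the crosstab answering Aim 1 cannot separate vulvodynia from female sex

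*Combined protocol and SAP*

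**What the plan says.** The Vulvodynia section describes a "condition that occurs in 8-10% of women of all ages", "characterized by localized pain in the vulva". The VU group is therefore entirely female.

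Nothing comparable limits the other three groups. The inclusion criteria cover age ("age range 18-65 years"), education and diagnosis. The exclusion criteria do not mention sex, and no section provides for matching or quotas. Men are expected: among the optional questionnaires, the sexual-function item "represents a differentiated questionnaire for females and males on sexual function".

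Aim 1 hypothesises that psychological profiles "characterize FM, CM, and VU groups compared to controls reporting other types of CP". The section on planned statistical analyses first compares the groups' sociodemographic make-up, partly "to select possible covariates based on selection bias". It then lists Two-Step clustering, and these steps:

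- "Crosstab analyses will be performed to test the association and their strength"
- "MANOVAs to detect differences in the classification variables based on cluster groups"
- Pearson correlations between clusters and other psychological domains

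None of these is described as adjusted, layered or restricted. The four-group ANOVA in the sample-size sentence names no covariate either.

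**The concern.** Covariates are to be selected, but no later step is said to use them. That matters most for sex, because for VU the imbalance is built into the design. Recruitment cannot remove it unless the other groups are also limited to women.

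The analysis that speaks to Aim 1 is the crosstab. The plan does not name its variables. Diagnosis by cluster is the natural reading, because Aim 1 compares diagnosis groups with controls, but it is an inference. On that reading, if women and men fall into the clusters in different proportions, VU will differ from a mixed-sex control group even when the disease has no effect. A finding presented as a VU-specific profile could then partly be a profile of being female, and the plan has no stated way to tell the two apart.

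The FM, CM and control groups may also differ from one another in sex mix. The background sections say that chronic pain and FM are more frequent in women and that migraine prevalence depends on sex.

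**Working it through.** **Inputs from the documents.** Four groups, 108 per group, 5% test, VU all women.

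**The plan's own figure.** Reading 0.35 as Cohen's f, a four-group ANOVA at 5% with 85% power needs 108 participants in total (27 per group, power 0.863), not 108 per group. That is a separate matter. The stated 108 per group is used below because it is the stated target.

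**Assumed, because the documents do not give it.**

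- w is the share of women among controls, taken as 60% to 90%.
- Cluster membership is a known yes/no.
- 50% of women, and 30% or 40% of men, belong to the cluster.
- Disease has no effect within either sex.

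**Step 1: spurious gap.** The VU share is 0.50. With 30% of men in the cluster, the control share is 0.50w + 0.30(1 − w), so the gap is 0.20(1 − w). This is 8, 6, 4 and 2 percentage points at w = 60%, 70%, 80% and 90%.

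**Step 2: how often the unadjusted VU-control 2×2 test rejects.** By hand at w = 60%:

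- control share 0.42, pooled share 0.46
- standard error = √(2 × 0.46 × 0.54 / 108) = 0.068
- shift = 0.08 / 0.068 = 1.18
- P(Z > 1.96 − 1.18) ≈ 0.22

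Pearson chi-square results, without the normal approximation:

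| Women among controls | 60% | 70% | 80% | 90% |
|---|---|---|---|---|
| Women 50%, men 30% | 21% | 14% | 9% | 6% |
| Women 50%, men 40% | 9% | 7% | 6% | 5% |

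With no men among controls the rate is 4.8%. With 27 per group and the stronger sex effect, it is about 8% at 60% women and 6% at 70%.

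**Step 3: the same contrast in women only.** The rejection rate is 5% at every w.

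**Step 4: FM, CM and controls (3×2 crosstab).** There is no inflation if the three share one sex mix (about 5%). With 90%, 80% and 65% women, the unadjusted test rejects in 10% (men 30%) or 6% (men 40%). Layered by sex (Cochran-Mantel-Haenszel), both return to 5%.

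**Step 5: one sex-adjusted logistic model for all four groups, VU against control.** If the sex effect is the same in every diagnosis, the rate is about 5%. If 50% of FM and CM men but 30% of control men are in the cluster, it is 12%, 8%, 6% and 5% at 60%, 70%, 80% and 90% women. VU has no men, so this model borrows its sex effect from the other groups.

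**Step 6: precision lost by restricting to women.** The standard error ratio is √[(1/108 + 1/(108w)) / (2/108)] = 1.155, 1.102, 1.061 and 1.027. Control men leaving number 108(1 − w), about 43, 32, 22 and 11.

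**The case against.** **The plan already provides for covariates.** If sex is recorded and the other groups include a fair number of men, the sociodemographic comparison will flag it. This stands as evidence of intent, so a reader should not infer that the plan ignores imbalance. It does not close the gap: a plain crosstab has no place for a covariate unless it is layered, and nothing says that it will be.

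**The size has no documentary basis.** This also stands. The background sections tie sex to how common the conditions are, not to personality, defences, central sensitization or trauma scores. They also point towards mostly female groups, where the problem is smallest. The 50% against 30% scenario is an assumption.

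**The calculation simplifies.** The plan names no VU-control 2×2 test, and its clusters are derived from twenty-two variables with no fixed number of clusters. The figures show the mechanism and its range. They are not error rates for this study.

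**Women-only contrasts go further than needed.** Sex adjustment in one model would do if the sex effect were common to all diagnoses. That cannot be checked for VU, which has no men, and Step 5 shows the consequence if it fails, although the inflation is modest above 70% women. What stands is the cost in interpretation: VU results would describe women, while FM and CM results would cover both sexes.

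**A stronger reading to avoid.** A reader might take 21% as the chance that VU falsely stands apart from FM, CM and controls together. It is not: it concerns one comparison, VU against controls, under the strongest assumptions shown.

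**Conclusion.** The point holds as a gap in the analysis plan that should be closed. Sex is tied to VU by design, men are foreseen elsewhere, and every listed analysis is unadjusted. If the crosstab is diagnosis by cluster, it cannot distinguish VU from female sex.

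The documents do not show that a VU finding would in fact be due to sex. That needs two things they do not give: an appreciable share of men among the comparison groups, and a sex difference in cluster membership. Under the assumptions above, the false-positive rate runs from 21% (60% women, strong sex effect) to about the nominal 5% (about 90% women). Contrasts among FM, CM and controls are affected only if those groups differ in sex mix.

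**What to change.** In the analysis section:

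1. State that sex is a survey item. The sociodemographic items are not listed, and the questionnaire is anonymous, so sex may not be recoverable later.
2. Make the diagnosis-by-cluster contrasts that involve VU in women only.
3. For contrasts among FM, CM and controls, layer the crosstab by sex or include sex in a logistic or multinomial model of cluster membership.
4. Keep the unadjusted four-group crosstab as description.

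An optional sensitivity check is to re-derive the clusters in women.

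The cost is two or three sentences and one further model or layered table; the optional check adds a second cluster run. Men leave the VU contrasts, and the standard error of the VU-control contrast rises by about 3% (90% women) to 15% (60% women). The report must say that VU contrasts describe women only, whereas FM and CM contrasts cover both sexes. The women's layer of a sex-layered table gives FM and CM results on the same footing as VU.

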### Rational

Chronic pain (CP), defined as pain lasting more than 3 months, is a substantial healthcare challenge. Prevalence rates of CP are between 11% and 40% (Dahlhamer et al., 2018). A systematic review reported a pooled CP prevalence rate of 43.5%, with the rate of moderate-to-severe disabling pain ranging from 10% to 14% (Fayaz et al., 2016). CP prevalence increases with age, is greater among females, and among people with lower socioeconomic status (Tsang et al., 2008; Pergolizzi et al., 2013). CP affects relationships and self-esteem, and is associated with higher divorce and suicide rates, and an increased risk of substance abuse (Tang et al., 2016; Fitzcharles et al., 2021), psychopathology (Katz et al., 2015) and risk of medication overuse (Westergaard et al., 2015). The causes of CP are still poorly understood. Recently, the International Association for the Study of Pain (IASP, 2017) has proposed that three subtypes of CP may be differentiated based on unique causal mechanisms: nociceptive, neuropathic, and nociplastic.

Nociplastic Pain (NP) is a new descriptor of CP and includes conditions that arise from altered nociception despite no clear evidence of actual or threatened tissue damage. NP should be viewed as an overarching terminology that can be applied to a diverse range of clinical conditions that share common neurophysiological mechanisms, involving various organ systems (Galli, 2023). Among nociplastic chronic

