#### CHRONIC MIGRAINE (CM)

Migraine affects ~15% of the general population globally and is typically characterized by recurring, often highly disabling attacks of severe headache, nausea, vomiting, super- sensitivity to light and sound, and other variable physical, mental, and psychological signs and symptoms, lasting for 4–72 h (Ferrari et al., 2022). Migraine is listed by The Global Burden of Disease Study as the third most disabling disease worldwide (Vos et al., 2012). Most patients have episodic migraine, although some patients develop CM (the presence of  $\geq 15$  headache days per month). The 1- year prevalence of migraine is 8–15% worldwide, but is highly dependent on age, sex, and migraine subtype (Ferrari et al., 2015). Migraine is 40–60% determined by genetic factors and for the remainder by non- genetic risk- modulating and trigger factors. Although a progressive increase of the attack frequency can occur spontaneously, it is often aggravated and/or induced by overuse of acute headache medications and/or caffeine. Risk factors for migraine progression toward CM include high headache frequency, high headache-related disability, obesity, allodynia, anxiety, and depression (Ferrari et al., 2022). Comorbid migraine and anxiety/depression are common in the general population, but the mechanism(s) supporting the comorbidity are still unknown. Overall, there seems to be a bidirectional relationship between migraine and depression, and a shared pathophysiological mechanism has been recently outlined (Karsan & Goadsby, 2021). Indeed, in cohort studies, the risk of incident migraine in persons with existing major depression was threefold higher than in persons without depression, and incident major depression in persons with pre- existing migraine was more than fivefold higher than in persons without migraine history (Modgill et al., 2011). Comorbid anxiety/depression increases the risk of migraine chronification (Guidetti et al., 1998; Tietjen et al., 2007). However, there is no evidence that treating depression or anxiety mitigates migraine (Ferrari et al., 2022). Other psychological factors have been linked to migraine over time, as the case of alexithymia (Galli et al., 2017, Bottioli et al., 2018), traumatic events (Bottioli et al., 2019; Stensland et al., 2013), early episodes of maltreatment (Tietjen et al., 2016), personality characteristics (Bottioli et al., 2016; 2021; Galli et al., 2019).

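### Selecting covariates by tests of group difference may often leave modest confounders out of the comparisons with controls; a fixed set and a named adjusted model are needed

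*Combined protocol and SAP*

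**What the plan says.** The section headed STATYSTICAL PLANNED ANALYSES gives one sentence to covariates. ANOVAs and chi-square analyses will compare "groups on sociodemographic characteristics for descriptive reasons" and, in the same step, will serve "to select possible covariates based on selection bias". It gives no p-value threshold, covariate list, standardised-difference rule or matching, and no other section supplies one.

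The comparison that these covariates would protect is in Aims. The hypothesis is that certain psychological factors "characterize FM, CM, and VU groups compared to controls reporting other types of CP (e.g., knee arthrosis, rheumatoid arthritis"). Participants come from specialist clinics and are grouped by diagnosis, so nothing balances the groups by design.

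The analyses named afterwards are cluster analysis, crosstabs, MANOVAs by cluster and Pearson correlations. None is described as taking a covariate.

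The background sections mention likely candidates: "CP prevalence increases with age, is greater among females, and among people with lower socioeconomic status" (Rational), and migraine prevalence is "highly dependent on age, sex, and migraine subtype" (CHRONIC MIGRAINE).

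**The concern.** Confounding needs two things: the variable differs between groups, and it is related to the score. A test of group difference addresses only the first, and answers it through sample size. A non-significant result means that the imbalance was not detected, not that it is harmless. A variable strongly related to the score can bias a contrast through an imbalance too small to reach significance.

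The study means to read differences between conditions and controls as areas of psychological sensitivity specific to each diagnosis, and to use them to direct treatment. Part of such a difference could come from age, sex or education.

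**Working it through.** **The plan's sample size.** The inputs are those of the statistical section: an ANOVA "having 4 groups (migraine, fibromyalgia, vulvodynia, and controls"), p = 0.05, "statistical power of 85%, and effect size of 0.35", giving 108 "participants per group (432 as total"). I read 0.35 as Cohen's f. With λ = N·f² and 3 and N−4 degrees of freedom, the smallest N is 105, or 108 in total when balanced (27 per group; λ = 108 × 0.1225 = 13.23; power 86.3%). The stated 108 per group is not reproduced; at N = 432, λ = 52.92 and power exceeds 99.9%. That is a separate matter. I use the stated 108 per group below and give 27 per group as a sensitivity.

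**How often the test misses an imbalance.** My assumptions, not in the documents: a variable is selected if p<0.05, and controls differ by d SD from the other three groups, which are equal.
- Variance of the four group means = [3(d/4)² + (3d/4)²]/4 = 3d²/16, so f = d√3/4.
- λ = 432 × 3d²/16 = 81d² at 108 per group.
- The variable is missed when the noncentral F(3, 428) falls below the critical value 2.63.

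| d (SD) | λ at 108 per group | Missed, 108 per group | Missed, 27 per group |
|---|---|---|---|
| 0.1 | 0.81 | 90% | 94% |
| 0.2 | 3.24 | 71% | 90% |
| 0.3 | 7.29 | 40% | 83% |
| 0.4 | 12.96 | 13% | 72% |
| 0.5 | 20.25 | 2.5% | 57% |

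For a binary covariate at 108 per group, 85% in three groups against 75% in controls is missed 51% of the time. With an all-female vulvodynia group (100/85/85/75% female) it is missed 0.2% of the time.

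**What a miss costs.** Leaving out one covariate with correlation r to the score biases the contrast by about r·d, for example 0.3 × 0.2 = 0.06 SD. Simulation used 3,000 to 6,000 studies per setting, 108 per group, independent covariates and no true diagnosis effect. It tested one condition against controls at 5%, with the covariates either screened or always included. Monte Carlo standard error near 5% is √(0.05 × 0.95/4000) ≈ 0.3 points at 4,000 studies.

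| Setting | Screened | Always included |
|---|---|---|
| One covariate, 0.2–0.3 SD, r = 0.3–0.5 | about 6–7% | about 5–6% |
| Four, 0.2 SD, r = 0.3, random directions | about 7% | about 5% |
| Four, 0.2 SD, r = 0.3, two up and two down | about 5% | about 5% |
| Three, 0.2 SD, r = 0.3, same direction | 11% | 5% |
| Four, 0.2 SD, r = 0.3, same direction | 16% | 5% |
| Four, no true imbalance, r = 0.3 | about 5% | about 5% |

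Mean residual bias under screening is 0.02 to 0.05 SD for one covariate, about 0.10 SD for three aligned and 0.13 SD for four aligned. It is about zero when the covariates are always included.

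At 27 per group, one covariate (0.2 to 0.5 SD) leaves 0.05 to 0.11 SD of bias on average. Four aligned covariates at 0.2 SD leave 0.19 SD, with type I error of 10%.

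The no-imbalance row locates the cause. The screen still operates there, yet the error rate stays at its nominal level. The excess in the other rows is therefore omitted confounding, not a penalty for ignoring the selection step.

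**The case against.** The strongest reply has five parts.

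- **No cut-off is stated.** This stands: the only p = 0.05 in the section belongs to the sample-size calculation. A reader might infer that the plan excludes any variable with p above 0.05, but the text does not say so. Without a cut-off, selection is left to judgement after the data are seen, which a fixed list also cures.
- **The large error rates need aligned biases.** This also stands. A reader might take 16% as the expected false-positive rate. It arises only when four imbalances all push the contrast the same way; mixed directions give about 7%, and exact cancellation about 5%.
- **The background does not establish confounding.** Correct. The Rational and CHRONIC MIGRAINE sections speak of prevalence in populations, whereas every group here, controls included, has chronic pain. They make age, sex and socioeconomic status reasonable candidates. They do not show a relation to the personality, defence, trauma or sensitisation scores; the correlations used above are assumptions.
- **Serious imbalances are caught.** True at 108 per group for 0.5 SD or for an all-female group, but less so at 27 per group, where 0.5 SD is missed 57% of the time.
- **No adjusted model is planned.** True, and a gap in its own right: selected covariates have nothing to enter. Naming a model without changing the selection rule would leave this problem in place.

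That unrelated variables may enter by chance is not a serious complaint; each costs about a degree of freedom and causes no bias.

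**Conclusion.** The point holds in a limited form. The plan makes tests of group difference the route for choosing covariates in a non-randomised comparison, and nothing elsewhere corrects this. Under an assumed p<0.05 screen, modest confounders (0.2 to 0.3 SD) would be left out in roughly 40 to 71% of studies of the stated size. The usual consequence is small: a few hundredths of an SD and a type I error of 6 to 7%. It reaches 11 to 16% only in the aligned worst case. These sizes rest on assumed imbalances, correlations and threshold, none of which the documents give. They do not show that the planned contrasts are badly biased. They show that the stated rule is worse than a fixed list that costs almost nothing.

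**What to change.** In the statistical section:

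1. Pre-specify age, sex and education, plus a socioeconomic indicator if the form collects one, as covariates in every condition-versus-control and cluster comparison of scores, whatever their p-values.
2. Name the model that takes them: ANCOVA or MANCOVA, or the equivalent regression.
3. Keep the ANOVA and chi-square tables as description only.
4. Vulvodynia participants will all be women, so sex does not vary in that group and adjustment borrows the sex effect from the other groups. Add a women-only sensitivity analysis for contrasts involving it.

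The cost is a few sentences and a few degrees of freedom out of 428. Age and education are already inclusion criteria, and sex is needed to assign the female or male sexual-function questionnaire.
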